8.6 Other Issues

Not applicable.

9. DEMOGRAPHICS AND BASELINE CHARACTERISTICS

Demographic and Baseline Characteristics will be summarized by randomized treatment group, and for the FA only.

Demographic data include age, gender, ethnicity, race, height, weight, body mass index (BMI) calculated as weight(kg)/height(m)² and illness severity score Acute Physiology and Chronic Health Evaluation II classification system (APACHE II).

Other baseline/screening data include:

- 1. Indication for CRRT (cause of AKI will be specified)
- 2. Known allergies
- 3. Current medications and medications prescribed during the 30-day period prior to informed consent
- 4. Medical history
- 5. Physical examination

- 6. Vital signs
- 7. Laboratory parameters

The following describes the summary of the various types of baseline data either as continuous data or as frequency tabulation:

- 1. Age will be summarized as a continuous variable across subjects, and as frequencies within age groups (18-35, 36-45, 46-55, 56-65, >65 years).
- 2. Height, weight, BMI and illness severity score APACHE II will be summarized as a continuous variable across subjects.
- 3. The frequencies for gender, ethnicity and race will be tabulated.
- 4. The frequencies for current medications and medications prescribed during the 30-day period prior to informed consent will be tabulated based on the medication names coded according to the WHO Drug Dictionary.
- 5. Physical examinations will be tabulated as those findings which are deemed: 'Normal', 'Abnormal, Not Clinically Significant', 'Abnormal, and Clinically Significant'.
- 6. Vital signs will be summarized as a continuous variable across subjects.
- 7. Laboratory parameters will be summarized as a continuous variable across subjects. Laboratory results will also be listed with clinical significance.

Continuous data will typically be summarized using the number of subjects n, mean, standard deviation, minimum, median and maximum. Treatment comparisons will be based on t-test or Wilcoxon rank sum test, as applicable. Frequencies will be compared between treatment groups utilizing Fisher's exact test.

The following describes the baseline data that will only be listed:

- 1. Indication for CRRT (including specification for AKI subjects)
- 2. Known allergies
- 3. Medical history including Medical Dictionary for Regulatory Activities (MedDRA) System Organ Class, MedDRA Preferred Term, medical condition/surgical procedure reported term, date of onset and information if the medical history is still present and if it was treated.

10. ANALYSIS OF PHARMACOKINETICS AND PHARMACODYNAMICS Not applicable.

11. TREATMENT COMPLIANCE AND EXPOSURE

Due to the ICU setting of the study, patient treatment compliance is not applicable.

Treatment exposure will be analyzed based on the percentage of the prescribed dose actually administered to the patient. Please refer to Section 13.3 Secondary Analysis for further details. Additionally, the number and percentage of subjects completing a certain overall CRRT treatment duration and the number and percentage of subjects using a certain number of extracorporeal circuits during the 120 hours evaluation period will be provided.

The number and percentage of subjects completing a certain extracorporeal circuit treatment time of the defined maximum 72 hours period for which each Prismaflex M150 Set can be used continuously along with reasons for treatment termination and location of clotting (Prismaflex M150 set or blood access device or in both) will be provided as well.

Overall CRRT treatment duration and the number of extracorporeal circuits used during the 120 hours evaluation period will be summarized using the number of subjects n, mean, standard deviation, median, minimum and maximum.

12. CHANGES IN CONDUCT OR PLANNED ANALYSES FROM THE PROTOCOL

No changes in conduct or planned analyses from the protocol.

13. EFFICACY PARAMETERS

13.1 Primary Analysis

The primary endpoint of the study, extracorporeal circuit life, will be analyzed as a time-to-event endpoint (survival analysis).

The extracorporeal circuit life of a filter that is replaced due to continuous use for 72 hours, will be censored for the statistical analysis. Likewise, filters that are in use when the end of the observation period of 120 hours is reached, will be censored at their current duration of usage at the end of the observation period. Filters that are replaced any time CRRT is stopped for reasons other than filter clotting (including drop-outs and switches to therapies other than Prismocitrate 18 or control), will be censored at their current duration of usage. Only filters that are replaced due to filter clotting or excessive transmembrane pressure as indicated by system alarms/conditions and confirmed by an Independent Adjudicator will be considered 'events' in the statistical survival analysis.

The context and data/time of two alarms (as below) used in the independent adjudication

- Warning: Filter Clotted" and/or
- "Advisory TMP Too High"

will be derived from the data card. The date and time of first occurrence of one or both alarms above that could not be successfully mitigated by the study site, will be considered as the end of the filter life if the event (alarm) is confirmed to be caused by filter clotting by the independent adjudicator. Also, the date and time recorded on data card for filter start, replace and/or end will be used to calculate the filter life during the independent adjudication.

If the reason for a filter change recorded on the eCRF is different from the indication from adjudication result (e.g. eCRF recorded a reason for filter change for any reasons other than the two alarm, but the adjudication result showed as filter clotted), the adjudication result will be used to determine if it is considered an 'event' in the statistical survival analysis.

In some scenarios, where no independent adjudication could be performed (e.g. missing data card file), the eCRF recorded filter start, end, and change reason will be used in the analysis of filter life.

Filters used after a patient crossed-over treatment to the other study treatment group (switch from Prismocitrate 18 to Control, or switch from Control to Prismocitrate 18) will be analyzed under the original, randomized treatment assignment following the intent-to-treat principle. Each filter used during the 120 hours observation period or until treatment is finished will be included in the statistical analysis (several filters per patient). The potential dependence between extracorporeal circuit lives within the same patient will be accounted for using a clustered log rank test.

Separate estimates per treatment group will be provided for the primary endpoint based on Kaplan-Meier methodology. These estimates of the survival functions will be graphically displayed and tabulated as cumulative distribution functions. Characteristic values of these functions such as Q1, median survival time and Q3, will be provided and differences between estimated survival functions will be assessed using a clustered log rank test ¹¹.

This clustered log rank test provides advantages over readily available methods to analyze clustered survival data, such as the PHREG procedure using the covariance sandwich estimator option and the NLMIXED procedure for accelerated failure time frailty models, both available in SAS, due to its complete non-parametric nature. No

assumptions about the distribution of the data or the structure of the covariance matrix have to be made. Details on the underlying clustered log rank test are provided in Section 13.1.1 Hypothesis Regarding Primary Endpoint.

Analyses of the primary endpoint will be carried out on the FA based on the randomized treatment groups (intent-to-treat principle) as well as the PP.

An interim analysis will be carried out after 50% of subjects completed treatment. Please refer to Section 13.5 Interim Analysis for further details regarding the interim analysis.

The study will be stopped early due to overwhelming efficacy when a p value of < 0.0087 is observed using the clustered log-rank test at the interim analysis (critical value based on Bauer & Koehne⁹ procedure with no early stopping for futility). If $p \ge 0.0087$ and the study continues enrollment into a second stage, Fisher's combination test will be performed at the end of the study using a critical value of 0.0087 (c_α) which guarantees that the overall Type I error is controlled and preserved at a maximum of 0.05:

$$p_1 p_2 \le c_\alpha = \exp\left[-\frac{1}{2}\chi_4^2(1-\alpha)\right]$$

where p_1 is the observed error probability for the test in the subsample of subjects investigated before the interim analysis,

and p_2 is the observed error probability for the test in the subsample of subjects enrolled after the interim analysis,

and $\chi_4^2(1-\alpha)$ is the $(1-\alpha)$ -quantile of the central χ^2 distribution with 4 degrees of freedom.

If $p_1 \le c_\alpha$ one could already stop at the interim analysis with the rejection of the null hypothesis since $p_2 \le 1$ holds per definition.

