6.7 Efficacy Variables

6.7.1 Primary Efficacy Endpoint

The Prismaflex M150 Set extracorporeal circuit life will be assessed as a time-to-event endpoint over a maximum 120 hours by the duration of time for which each Prismaflex M150 Set can be used continuously over a maximum 72 hour period in each patient. The Prismaflex M150 Set will be replaced any time CRRT is stopped during the Treatment Period (regardless of duration) or any time a circuit is used for 72 continuous hours (ie, "Advisory Time to Change Set"). The end of the extracorporeal circuit life will be defined by the occurrence of one or both of the following Prismaflex System alarms/conditions if the alarm cannot be mitigated. At this point, study CRRT will be terminated and the extracorporeal circuit replaced because mitigation of the following alarms is not possible:

- "Warning: Filter Clotted", and/or
- "Advisory TMP Too High"

Note: The nurse at the clinical site will document the alarm and rationale to stop treatment on the eCRF. In addition, the Prismaflex logging information from the data cards (one card per patient) will be collected on an ongoing basis and anonymized data will be sent to Baxter for technical analysis. An Independent Adjudicator will make the final determination of the alarm cause by examining the applicable historical electronic data available surrounding the alarm events (see Section 9.9 Primary Endpoint Adjudication).

The extracorporeal circuit life will be censored for cases where the Prismaflex M150 Set has been replaced for reasons other than reaching the end of the extracorporeal circuit life. Only filters for which the end of the extracorporeal circuit life was reached (ie, one or both Prismaflex System alarms/conditions occurred as defined above and alarm causes have been confirmed by an Independent Adjudicator) will be considered 'events' in terms of the statistical analysis.

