8.3 Analysis Populations

The Full Analysis (FA) Set will include all randomized patients who received any study treatment for any period of time.

All analyses will be performed on the FA Set unless otherwise noted.

In addition to the FA Set, a Per Protocol (PP) Set will be used to check the robustness and validity of the primary analysis by repeating the analysis on the PP Set as a sensitivity analysis.

The PP Set defines a subset of the FA Set including patients who:

- fulfill all inclusion criteria.
- do not meet any of the exclusion criteria.
- were randomized and treated according to the randomization scheme.
- received at least 80% of their prescribed CRRT dose.
- do not have major protocol deviations that might impact the assessment of the primary endpoint (eg, mechanical malfunction of the machine).
- have available survival data for extracorporeal circuit life of at least one circuit
 (ie, time to occurrence of Prismaflex System alarms/conditions as outlined in
 Section 6.7.1 Primary Efficacy Endpoint and alarm cause determined and
 confirmed by Independent Adjudicator as outlined in Section 9.9 Primary
 Endpoint Adjudication, or censored circuit life if no system alarms/conditions
 occurred until the circuit was used for 72 continuous hours or if CRRT was
 stopped during the Treatment Period for reasons other than system
 alarms/conditions or if Independent Adjudicator did not confirm the alarm cause).

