8.5 Efficacy Endpoints

8.5.1 Primary Efficacy Endpoint

The primary endpoint of the study, extracorporeal circuit life, will be analyzed as a time-to-event endpoint (survival analysis).

In the statistical analysis extracorporeal circuit life of a filter that is replaced due to continuous use for 72 hours, will be censored. Likewise, filters that are in use when the end of the observation period of 120 hours is reached, will be censored at their current duration of usage at the end of the observation period. Filters that are replaced any time CRRT is stopped for reasons other than filter clotting (including drop-outs), will be censored at their current duration of usage. Only filters that are replaced due to filter clotting or excessive transmembrane pressure as indicated by one or both Prismaflex System alarms/conditions as defined under Section 6.7.1 Primary Efficacy Endpoint and for whom alarm causes have been confirmed by an Independent Adjudicator, will be considered 'events' in terms of the statistical analysis.

Each filter used during the 120 hours observation period or until treatment is finished will be included in the statistical analysis (several filters per patient).

Separate estimates per treatment group will be provided for the primary endpoint based on Kaplan-Meier methodology. Differences between treatment groups will be assessed using a clustered log-rank test in order to account for the potential dependence among extracorporeal circuit lives of the same patient.[19]

Analyses of the primary endpoint will be carried out on the FA Set based on the randomized treatment groups (intent-to-treat principle).

An interim analysis will be carried out after 50% of subjects completed treatment. Please refer to Section 8.8 for further details regarding the interim analysis.

The study will be stopped early due to overwhelming efficacy when a p value of < 0.0087 is observed using the clustered log-rank test at the interim analysis, see section 8.8 (critical value based on Bauer & Kohne procedure with no early stopping for futility). If $p \ge 0.0087$ and the study continues enrollment into a second stage, Fisher's combination test will be performed at the end of the study using a critical value of 0.0087 which guarantees that the overall type 1 error is controlled and preserved at a maximum of 0.05.[18]

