6.2.2 Per-Protocol Analysis Set (PP)

The Per-Protocol Analysis Set (PP) defines a subset of the FA including patients who

- fulfill all inclusion criteria
- do not meet any of the exclusion criteria
- were randomized and treated according to the randomization scheme
- received at least 80% of their prescribed CRRT dose
- do not have major protocol deviations that might impact the assessment of the primary endpoint (e.g., mechanical malfunction of the machine)
- have available survival data for extracorporeal circuit life of at least one circuit
 (i.e., time to occurrence of Prismaflex System alarms/conditions as outlined in
 Section 5.5.1 Primary Efficacy Endpoint, or censored circuit life if no system
 alarms/conditions occurred until the circuit was used for 72 continuous hours or if
 CRRT was stopped during the evaluation period for reasons other than system
 alarms/conditions).

The Per Protocol Set will be analyzed based upon the subjects randomized treatment.

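### Where adjudication is impossible, the unblinded site's eCRF reason decides primary events and no planned run tests this; the stage split and schedule footnote e also need correcting (minor)

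*SAP*

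**What the plan says.** **Event rule.** Protocol 6.7.1 counts a filter as an event only if an alarm occurred and "alarm causes have been confirmed by an Independent Adjudicator". Protocol 8.5.1 limits events to filters "for whom alarm causes have been confirmed by an Independent Adjudicator". SAP 5.5.1 repeats the rule. SAP 13.1 says that only filters replaced for clotting or "excessive transmembrane pressure as indicated by system alarms/conditions and confirmed by an Independent Adjudicator will be considered" events. None of these statements has an exception.

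**Two rules for difficult cases, both in SAP 13.1.** If the eCRF and the adjudicator disagree, "the adjudication result will be used to determine if it is considered an" event. If no adjudication could be performed, "the eCRF recorded filter start, end, and change reason will be used in the analysis of filter life".

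**Who writes the eCRF reason.** Protocol 6.7.1: "The nurse at the clinical site will document the alarm and rationale to stop treatment on the eCRF". Protocol 5.5 makes the trial open-label, so the site team knows the assignment. Protocol 9.9 keeps the adjudicator blinded. There is one data card per patient.

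**Per Protocol definitions.** Protocol 8.3 includes, among its censored cases, "or if Independent Adjudicator did not confirm the alarm cause". SAP 6.2.2 stops at the case where "CRRT was stopped during the evaluation period for reasons other than system" alarms or conditions, and has no adjudicator clause. SAP 12 declares no change from the protocol.

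**Stages.** SAP 13.1 bases p1 on subjects investigated before the interim. SAP 13.1.1 bases p1 on subjects who have completed treatment at the interim and p2 on subjects enrolled after it.

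**Footnote e** (Protocol Appendix 2 and SAP Table 1) says that an unmitigated alarm ends the patient's treatment period. Protocol 5.2, 6.7.1 and 8.5.1 and SAP 5.5.1 and 13.1 instead have the circuit replaced and several filters per patient analysed over up to 120 h.

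**The concern.** Blinded confirmation is what protects a machine-alarm endpoint in an open-label trial. The fallback moves some circuits from a masked source to an open-label one, and a lost card can affect all of that patient's circuits. The harmful error is a Control stop for some other reason that the site records as clotting. An eCRF reason of clotting (Protocol 7.4.7) also need not correspond to an alarm that the adjudicator would have attributed to filter clotting.

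The planned checks do not isolate this. The four scenarios in SAP 13.2 recode only filters stopped for reasons other than clotting, so a site-called clot stays an event in all four. The PP analysis repeats the 13.1 rule. At stake is whether a reader can see how many outcomes rest on site calls, and whether the result holds without them.

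The two wording errors matter for other reasons. One leaves a patient's stage undefined in a two-stage test. The other, if a site followed it, would stop data collection at the first clot.

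**Working it through.** **The plan's own figure.** The critical value is exp(-½ × χ²₄(0.95)) = exp(-9.488/2) = 0.0087, as stated. The overall level is c(1 - ln c) = 0.0087 × (1 + 4.744) = 0.050. The power above 90% cannot be recomputed, because its inputs are blacked out.

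**(a) How many circuits could be affected.** The documents give no missing-card rate, clotting rate or non-clot stop rate, so all of these are assumed: 80 patients per arm, Control median circuit life 24 h with gamma frailty variance 0.5, removal for other causes 0.006/h, exponential dropout with mean 120 h, a 72 h cap and a 120 h window.

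- Mean observed time: 120 × (1 - e⁻¹) = 75.9 h.
- Mean clotting rate θ, from (1 + 0.5 × 24θ)⁻² = 0.5: θ = 0.0345/h. Control clots: 0.0345 × 75.9 × 80 ≈ 210.
- Control removals for other causes: 0.006 × 75.9 × 80 ≈ 36.4 (simulated 36.5).
- Control dropouts during treatment: 80 × (1 - e⁻¹) ≈ 50.6 (simulated 50.9). SAP 13.1 treats these as non-clot stops.
- Control non-clot stops: 36.5 + 50.9 = 87.4. With 5% or 10% of cards missing, 0.05 × 87.4 = 4.4 or 0.10 × 87.4 = 8.7 lack adjudication, beside about 210 Control clots.
- Both arms together have about 673 simulated circuits, of which 34-67 would lack adjudication.

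**(a) Effect on false positives.** The test was simulated under no true effect as two stages of 40 + 40 per arm, rejecting if p1 < 0.0087 or p1·p2 < 0.0087, with cards lost by patient and only Control stops miscalled. With full adjudication the simulated rate is 5.4%.

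| Assumptions | Cards missing | Result |
|---|---|---|
| Rates above; removals and dropouts can be miscalled (4,000 paired trials) | 5% | change -0.08 (half miscalled), +0.15 (all) points |
| Same | 10% | change +0.03 (half), +0.65 (all) points |
| Non-clot stops more frequent (median 40 h), other rates as above | 5-10% | 5.6-6.4% |
| Same, all miscalled | 20% | up to 8.9% |
| Median 40 h to a non-clot stop, both circuit medians 30 h, frailty variance 0.3, no dropout (1,500 trials; 4.6% with no cards missing) | 5-10% | 5.7-8.1% |
| Same | 20% | 8.7-16.3% |

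Standard errors are 0.14-0.28 points for the paired changes in the first two rows and about 0.6 points for the last two rows. In the extreme case of +0.65, a true rise near 1 point is not excluded.

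**(b) Patients on treatment at the interim cut.** Planned accrual is 160 patients in about 48 months, or 3.33 per month. With the full 5 days of treatment: 3.33 × 5/30.4 = 0.55 patient expected, and 1 - e^(-0.55) = 42% chance of at least one. With mean treatment of 76 h: 0.35 patient and 29%.

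**(c) Footnote e taken literally.** Under the same assumed Control rates, a patient handled by the footnote contributes 0.7 clot events instead of 2.6, and 29 observed hours instead of 76.

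**The case against.** The fallback is pre-specified, is confined to circuits that could not be adjudicated, and gives way to the adjudicator wherever a ruling exists. Protocol 8.1 asks the SAP to elaborate methods and set analysis conventions, and a rule for a missing source file can be read that way. Safeguards exist: SAP 6.3 makes improper assessment of the primary endpoint a ground for PP exclusion, SAP 11 tabulates termination reasons and clot location, and Listing 16.2.9.12 shows adjudication results. Scenarios 1 and 2 in SAP 13.2 already cover Prismocitrate clots recorded as other stops.

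Most of this stands, and it keeps the point minor. It does not supply the missing check. The SAP 6.3 criterion is not tied to missing cards, a listing is not a summary by arm, and no scenario censors a site-called clot. Scenario 1 is free of the site label only because it turns every non-clot stop in the trial into an event.

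Some stronger readings are tempting, but the documents do not support them:

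- A reader might infer that Protocol 8.3 requires unadjudicated circuits to be censored. Its clause sits in a PP eligibility item and most naturally means an alarm that was reviewed and not confirmed. Its absence from SAP 6.2.2 changes no event rule.
- A reader might infer that SAP 12 conceals a change. The visible change history for version 4.0 is incomplete, so this cannot be checked.
- A reader might infer that open-label calls invalidate the primary test. That would need many missing cards and one-sided coding, and the documents indicate neither.
- A reader might infer from footnote e that only first circuits count, or from SAP 13.1.1 that patients are meant to be dropped. The body text in both documents contradicts the first reading, and an exhaustive split is clearly intended.

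**Conclusion.** Minor.

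(a) The event rule and its fallback conflict, and the affected site-called clots go untested. The size is unknown and probably small. With 5-10% of cards missing and Control-only miscalls, every estimated rise at the base rates is below 1 point. With more frequent non-clot stops or 20% or more of cards missing, it could reach several points or more. All of this rests on assumed rates for clotting, other stops, dropout and lost cards.

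(b) Under one patient is expected to be affected, but the stage must be defined.

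(c) Footnote e is wrong as written. Sites are unlikely to follow it given the body text, but the loss would be large for each patient handled that way.

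**What to change.** **(a)** Keep the eCRF rule as primary. Report by arm the number of circuits without data-card adjudication and the site-called clots among them, next to Listing 16.2.9.12. Add one supportive FA run of the primary test that censors every site-called clot lacking data-card adjudication. If masked eCRF data are later reviewed for such a circuit, it stays in the censored set, because the site's entry still drives the ruling. List the rule in SAP 12.

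*Cost:* SAP text, one count table and one rerun. The run has less power than the primary analysis: with 10% of cards missing, 98% falls to 95% for assumed medians of 45 vs 25 h, and 56.6% falls to 46.8% for assumed medians of 36 vs 24 h. If cards are missing in Control only, the run is biased against citrate, with a null hazard ratio of 1.05 (5% missing) or 1.11 (10%). It is therefore supportive only.

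**(b)** In SAP 13.1.1, define stage 1 as all patients randomised up to the interim cut, each followed to the end of treatment, and stage 2 as all patients randomised afterwards. State how the cut date is set. *Cost:* one or two sentences, and a wait of up to 120 h of study CRRT for any patient on treatment at the cut.

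**(c)** In footnote e of both documents, delete the clause that ends the patient's treatment period, and state that the circuit is replaced and study CRRT continues up to 120 h. *Cost:* one correction in each document.
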